**Table 11-3: Required investigations and follow up for PDILI**

Laboratory value			Immediate		Follow up	
ALT or AST	Total bilirubin	Symptoms a of hepatitis or hypersensitivity	Consultation requirements	Actions	Testing	Evaluation
≥3xULN	≥2xULN b	NA	Hepatology consult. c	Immediate, permanent IMP discontinuation.	Essential: Must have repeat liver chemistry values and additional testing completed ASAP (see Section 11.6.1.3); recommended to occur at the site with HCP.	Monitoring of liver chemistry values at least twice per week until values normalize, stabilize, or return to within baseline values. d
≥8xULN	NA	Medical Monitor must be notified within 24 hours (eg, by laboratory alert) and subject discussed with Medical Monitor ASAP.	Immediate, temporary or permanent, IMP discontinuation.			
≥3xULN	NA	Yes				
≥3xULN (and ≥2x baseline) and <5xULN	<2xULN	No	Discussion with Medical Monitor required if the criterion that allows for IMP continuation is met.	Further investigation and immediate IMP discontinuation not required (see Section 11.6.1.2).	Not required unless otherwise medically indicated (at discretion of Investigator).	
≥5xULN (and ≥2x baseline)	<2xULN	No	Discussion with Medical Monitor required.	Immediate, permanent IMP discontinuation.	Essential: Every attempt must be made to have repeat liver chemistry values and additional testing completed within 48 hours at the site with HCP (see Section 11.6.1.3).	Monitoring of liver chemistry values at least twice per week until values normalize, stabilize, or return to within baseline values. d

---

ALP=alkaline phosphatase; ALT=alanine aminotransferase; ASAP=as soon as possible; AST=aspartate aminotransferase; HCP=healthcare practitioner; IMP=investigational medicinal product; NA=not applicable; PDILI=potential drug-induced liver injury; ULN=upper limit of normal.

a Hepatitis symptoms include fatigue, nausea, vomiting, and right upper quadrant pain or tenderness; hypersensitivity symptoms include eosinophilia (>5%), rash, and fever (without clear alternative cause).

b If the subject also has  $\geq 2 \times$ ULN ALP, the possibility of an indication of biliary obstruction should be discussed with the Medical Monitor.

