## **13.4 Planned safety and other analyses**

### **13.4.1 Safety analyses**

Adverse events will be coded using the Medical Dictionary for Regulatory Activities (MedDRA®). Adverse events will be summarized by MedDRA System Organ Class and Preferred Term. The incidence of SAEs, AEs leading to premature discontinuation or dose tapering, and related AEs, and the incidence of AEs by maximum intensity, will also be summarized.

Laboratory values, ECG data (heart rate, PR interval, QRS duration, QT interval, QTcB or QTcF, and Investigator's conclusion on ECG profile) and arrhythmias, vital signs, weight, and changes from Baseline in these measures will be summarized by period, visit, and treatment group. Possibly clinically significant treatment-emergent abnormalities for laboratory values, vital signs, and weight will be listed and summarized by period and visit for each treatment group.

Electrocardiogram abnormalities as well as physical and neurological abnormalities will also be listed by period and visit. Quantitative safety parameters will be summarized descriptively by time point and treatment group. Categorical safety summaries will provide the number and percentage of subjects within each summarized category.

Doppler echocardiogram results at Baseline and during and after treatment, and changes from Baseline, will be listed and descriptively summarized.

All C-SSRS data obtained at Baseline and subsequent visits will be reported as a listing ordered by subject and visit. Psychiatric and Mental Status assessment and CIWA-B data will also be included using listings.

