3.2.2.2 End of the 16-week treatment period

The end of the 16-week overall treatment period will be either the date of Visit 7 for subjects completing the Treatment Period, or the date of the early discontinuation visit (EDV), for subjects who discontinued during the Treatment Period. If a subject does not have a Visit 7/EDV, then the date of the last contact will define the end date of the Treatment Period.

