10.3 Clinical laboratory evaluations

Clinical laboratory hematology, chemistry and urinalysis measurements obtained from blood/urine samples collected throughout the study are presented in Table 10-1.

During the study, non-protocol-specified lab parameters (unplanned) may be collected. Summaries of lab parameters will only include planned parameters as specified in the protocol. All lab parameter values will be listed and summarized using international units.

The observed value and change from Baseline will be summarized descriptively by treatment group and PSL total group and scheduled study visit. The Last Visit, minimum, and maximum post-baseline values during the Treatment Period will also be included. These summaries will be organized by lab function panel and parameter.

Shift from Baseline to the maximum and minimal values during the Treatment Period based on normal range (Low, Normal, High) will be provided for hematology and blood chemistry parameters in Table 10-1.

Possibly clinically significant treatment-emergent (PCST) criteria have been developed based on FDA Division of Neuropharmacologic Drug Products guidelines with some UCB-defined additions and are provided in Appendix 13.1. For lab parameters with PCST criteria, the number and percentage of subjects with a PCST value at any time (scheduled and unscheduled visits) during the Treatment Period will be summarized by treatment group and PSL total group. . Treatment-emergent values are those occurring any time on or after the first dose of study medication in EP0092. Subject numbers for those meeting the PCST criteria will also be presented.

Table 10–1: Laboratory measurements

Hematology	Chemistry	Urinalysis
Basophils	ALP	Glucose
Eosinophils	ALT	pH
Hematocrit	AST	RBC
Hemoglobin	Bilirubin	Total protein
Lymphocytes	BUN or urea	WBC
MCH	Calcium	Microscopy (WBC, RBC, casts, crystals, bacteria) ^a
MCHC	Chloride	Other
MCV	Creatinine	FSH ^b
Monocytes	Glucose	
Neutrophils	HDL	
Platelet count	LDH	
RBC count	LDL	
WBC count	Magnesium	
	Potassium	
	Sodium	
	Total bilirubin	
	Total cholesterol	

ALP=alkaline phosphatase; ALT=alanine aminotransferase; AST=aspartate aminotransferase; BUN=blood urea nitrogen; HDL=high density lipoprotein; FSH=follicle stimulating hormone; LDH=lactate dehydrogenase; LDL=low density lipoprotein; MCH=mean corpuscular hemoglobin; MCHC=mean corpuscular hemoglobin concentration; MCV=mean corpuscular volume; RBC=red blood cell; WBC=white blood cell

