10.3.1 Subjects with potential drug-induced liver injury (PDILI)

There are specific criteria described in the protocol Section 11 to evaluate subjects for potential drug-induced liver injury (PDILI). The evaluations required by protocol for PDILI subjects are collected on the following CRFs:

- Most Recent Study Medication Administration, for PDILI
- Laboratory Tests DILI
- Vital Signs DILI
- Hepatic Event Supplemental Medical History for PDILI

- Potential Hepato-Toxic Medications Inquiry for PDILI
- Symptoms of Hepatitis and Hypersensitivity for PDILI
- Lifestyle PDILI
- Family Medical History for PDILI

Listings will be prepared presenting subjects with PDILI data. A summary of number and percent of subjects meeting PDILI criteria (ALT, AST, total bilirubin, ALP, and presence of symptoms) during the Treatment Period (scheduled and unscheduled visits) will be provided following the UCB standard table shell for PDILI Data. Subjects who met these criteria will be listed.

ALT Criteria	AST Criteria	Total Bilirubin Criteria	ALP Criteria	Presence of Symptoms
≥3xULN	≥3xULN	≥2xULN	≥2xULN	NA
≥8xULN	≥8xULN	NA		NA
≥3xULN	≥3xULN	NA		Y
≥3xULN <5xULN and ≥2x Baseline	≥3xULN <5xULN and ≥2xBaseline	<2xULN		N
≥5xULN <8xULN and ≥2x Baseline	≥5xULN <8xULN and ≥2xBaseline	<2xULN		N
≥5xULN and ≥2xBaseline	≥5xULN and ≥2xBaseline	<2xULN		N

N=No; NA=Not Applicable; ULN= upper limit of normal; Y=Yes.

A summary table highlighting the potential cases of Hy's Law, within each treatment group will be presented.

Potential Hy's Law, is defined as ≥3xULN ALT or AST with coexisting ≥2xULN total bilirubin in the absence of ≥2xULN ALP, with no alternative explanation for the biochemical abnormality.

In order to meet the above criteria, a subject must experience the elevation in bilirubin and ALT or AST at the same visit. For example, a subject who experiences a ≥2 x ULN elevation of bilirubin at one visit and a 3 x ULN elevation in ALT (or AST) at a subsequent visit has not fulfilled the Hy's law criteria.

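### Laboratory, liver-criteria and vital-sign/weight threshold counts stop at the end of the Treatment Period, so threshold values in Conversion, Taper and follow-up enter no such count

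*SAP*

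**What the plan says.** SAP 10.3.1 plans a table of subjects meeting the PDILI criteria, which "during the Treatment Period (scheduled and unscheduled visits) will be provided following the UCB standard table shell for PDILI Data". SAP 10.3 says that "the number and percentage of subjects with a PCST value at any time (scheduled and unscheduled visits) during the Treatment Period will be summarized". SAP 10.4.1 confines the abnormal vital-sign and body-weight counts to the same period.

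SAP 3.2.2.2 fixes where that period stops. For a completer, the last day is Visit 7. For anyone who stops early, it is "the date of the early discontinuation visit (EDV), for subjects who discontinued during the Treatment Period". Where neither visit took place, "the date of the last contact will define the end date of the Treatment Period". SAP Table 3-1 starts Conversion, and Taper and Safety Follow-up, on the following day.

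Protocol 13.4.1 says that possibly clinically significant treatment-emergent abnormalities in laboratory values, vital signs and weight "will be listed and summarized by period and visit for each treatment group". SAP 3.9, which lists the changes to protocol-defined analyses, does not mention a narrower window. SAP 10.3 also defines a treatment-emergent laboratory value as one at any time from first dose, with no end date.

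The potential Hy's Law table in SAP 10.3.1 is described separately and has no stated window. Its only timing condition is that the transaminase and bilirubin rises occur at the same visit.

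**The concern.** The window closes while many subjects are still on study drug. Under Protocol 5.1 the taper starts at Visit 7 or the EDV, so for a tapering subject that visit opens a further on-drug period. Converters stay on drug for three more weeks, and under Protocol 7.2.3 placebo subjects begin active PSL then. A threshold laboratory value, vital sign or weight change in these weeks is counted in none of the three tables.

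Liver follow-up is also affected. Protocol 6.3.1 requires permanent discontinuation at ALT or AST of 5xULN or more, and Protocol Table 11-3 then requires "Monitoring of liver chemistry values at least twice per week until values normalize, stabilize, or return to within baseline values". Samples from that monitoring that fall after the EDV are outside the PDILI and PCST counts. If bilirubin first reaches 2xULN then, with ALT or AST still at 3xULN or more, the subject stays in a transaminase-only row of the PDILI table.

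**Working it through.** **1. Reproduce the plan's own durations** (Protocol 5.1, 5.1.1 and Table 5-1).

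- Maximum exposure: 16 weeks of Treatment + 3 weeks of Conversion (or 3 weeks of on-drug taper) = 19 weeks. The protocol states 19.
- Study duration: 4 weeks of Baseline + 23 weeks from Day 1 to the follow-up visit = 27 weeks. The protocol states 27.

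**2. Time outside the counting window**, for a subject who reaches Week 16.

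- Converter: Week 19 - Week 16 = 3 weeks, all on drug.
- Tapering subject: Week 23 - Week 16 = 7 weeks, of which 3 are on drug.
- Share of planned exposure outside: 3/19 = 15.8%.

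**3. Scheduled post-dose laboratory draws outside the window** (Protocol Table 5-1 and Sections 8.2.3 to 8.4).

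- Converter: Visits 4, 6, 7 and 8. Visit 8 is outside: 1/4 = 25%.
- Tapering subject: Visits 4, 6, 7, 8 and 9. Visits 8 and 9 are outside: 2/5 = 40%.

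Converters leave the study at Visit 8, so the 30-day follow-up visit does not apply to them.

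**4. What other outputs show after the window closes.**

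- *By-visit laboratory summaries* (SAP 3.1 and 10.3) include scheduled visits, with Visit 8 split between Conversion and Taper/follow-up. They describe observed values and changes, without counting threshold crossings, and they exclude unscheduled samples.
- *Minimum, maximum and shift tables* (SAP 10.3) are limited to the Treatment Period.
- *Treatment-emergent adverse events by period* (SAP 10.2) cover Conversion and Taper/follow-up, and Protocol 11.6.1 requires every PDILI event to be reported as an adverse event. These tables count preferred terms and do not apply ALT, AST or bilirubin thresholds. The serious-event tables by period omit Conversion and Taper/follow-up, and the relationship and intensity tables cover only the Treatment Period.
- *Listings* show the values but give no rate by treatment group.
- *The potential Hy's Law table* may or may not include later cases, because no window is given.

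An unscheduled liver sample taken after the EDV therefore enters no by-visit table and neither the PDILI nor the PCST count.

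**5. What still counts after a liver stop.** The window closes at the EDV rather than at last dose. The last-dose cut in SAP Table 3-1 concerns seizure data only. Unscheduled samples between the stop and the EDV are counted, and a subject with no EDV is counted to last contact. Protocol 6.3.1 keeps PDILI subjects in the study until monitoring is complete, but nothing ties the EDV to that point.

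**The case against.** The strongest reply is that the Treatment Period is the only part of the study with a randomised placebo comparison. After Visit 7, placebo converters receive PSL and all converters move to one common dose. A single count from first dose to final contact, shown by randomised arm, would put PSL-exposed events in the placebo column and could dilute a signal. This stands: it is a good reason to keep the Treatment Period count and to keep later periods separate from it. It is no reason to leave the later periods out.

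A second reply is that little is hidden, since later values are listed, scheduled values are summarised, and liver events can be counted as adverse events. This also stands, and it limits the point to missing threshold counts. A reader might infer that later liver values are never counted, or that every bilirubin rise after a liver stop is missed. The documents do not support either. Values up to the EDV are inside the window, and a later joint rise that meets the definition may enter the Hy's Law table as written.

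Third, Protocol 13.4.1 names laboratory, vital-sign and weight abnormalities. It does not name PDILI criteria or Hy's Law. That is correct: the departure from the protocol covers the first group only, and extending the PDILI table is a recommendation on its merits.

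**Conclusion.** The point holds as a gap in the threshold tables. PCST, PDILI and vital-sign/weight counts omit everything after Visit 7 or the EDV. That is up to 3 of 19 planned exposure weeks, 1 of 4 scheduled post-dose laboratory draws for converters, and 2 of 5 for completers who taper. For PCST and vital-sign/weight abnormalities it is an unrecorded departure from Protocol 13.4.1, and it fits poorly with the SAP's open-ended definition of treatment-emergent laboratory values. For the potential Hy's Law table the defect is an unstated window.

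The figures assume nominal visit timing, completion of Week 16 and a three-week taper. Visit windows, a faster or slower taper, or early discontinuation would change them. They are shares of time and of scheduled draws, and say nothing about how many liver events would be missed. A reader might also infer that under-counting would be worst in the arms with more liver-related stops. The documents give no figures by arm to support that.

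**What to change.** In the SAP:

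- Keep the Treatment Period count in 10.3, 10.3.1 and 10.4.1 as the randomised comparison.
- Add separate Conversion and Taper/follow-up rows to the PCST, PDILI and vital-sign/weight tables, including unscheduled samples and PDILI follow-up samples. Use the subjects entering each period as the denominator.
- Show placebo-to-PSL converters as their own group, not under placebo, in Conversion and in any later taper.
- State that the potential Hy's Law table runs from first dose to final contact, split by period in the same way.
- Record in 3.9 any remaining departure from Protocol 13.4.1.

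The data are already collected and the periods already defined in SAP Table 3-1, so the cost is SAP wording and a few table rows. The downside is that follow-up after Week 16 differs between subjects and is not a randomised comparison, so the added rows should carry a note saying so.

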### **6.3.1 Potential drug-induced liver injury IMP discontinuation criteria**

Subjects with potential drug-induced liver injury (PDILI) must be assessed to determine if IMP must be discontinued. In addition, all concomitant medications and herbal supplements that are not medically necessary should be discontinued.

The PDILI criteria below require immediate and permanent discontinuation of IMP:

- Subjects with either of the following:
  - ALT or AST  $\geq 5\text{x ULN}$
  - ALT or AST  $\geq 3\text{xULN}$  and coexisting total bilirubin  $\geq 2\text{xULN}$

The PDILI criterion below requires immediate discontinuation of IMP:

- Subjects with ALT or AST  $\geq 3\text{xULN}$  who exhibit temporally associated symptoms of hepatitis or hypersensitivity. Hepatitis symptoms include fatigue, nausea, vomiting, and right upper quadrant pain or tenderness. Hypersensitivity symptoms include fever (without clear alternative cause), rash, or eosinophilia (ie,  $>5\%$ ).

If a nondrug-related cause for the symptoms can be confirmed, these subjects may resume IMP administration after discussion with the responsible UCB physician, but only when the requirements for rechallenge with IMP as provided in Section 11.6.1.2.1 are followed.

The PDILI criterion below allows for subjects to continue on IMP at the discretion of the Investigator.

- Subjects with ALT or AST  $\geq 3$ xULN (and  $\geq 2$ x baseline) and  $< 5$ xULN, total bilirubin  $< 2$ xULN, and no eosinophilia (ie,  $\leq 5\%$ ), with no fever, rash, or symptoms of hepatitis (eg, fatigue, nausea, vomiting, and right upper quadrant pain or tenderness).

Evaluation of PDILI must be initiated as described in Section 11.6.1. If subjects are unable to comply with the applicable monitoring schedule, IMP must be discontinued immediately.

Investigators should attempt to obtain information on subjects in the case of IMP discontinuation to complete the final evaluation. Subjects with PDILI should not be withdrawn from the study until investigation and monitoring are complete. All results of these evaluations and observations, as well as the reason(s) for IMP discontinuation and subject withdrawal (if applicable), must be recorded in the source documents. The eCRF must document the primary reason for IMP discontinuation.

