### 11.1.1.3 Adverse events of special interest

An AE of special interest is any AE that a regulatory authority has mandated be reported on an expedited basis, regardless of the seriousness, expectedness, or relatedness of the AE to the administration of a UCB product/compound.

Potential Hy’s Law, defined as  $\geq 3 \times \text{ULN}$  ALT or AST with coexisting  $\geq 2 \times \text{ULN}$  total bilirubin in the absence of  $\geq 2 \times \text{ULN}$  ALP, with no alternative explanation for the biochemical abnormality, must ALWAYS be reported to UCB as an AE of special interest (ie, without waiting for any additional etiologic investigations to have been concluded). Follow-up information should then be reported if an alternative etiology is identified during investigation and monitoring of the subject.

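### SAP 10.3.1 counts potential Hy's Law one visit at a time, so a bilirubin rise that follows after ALT/AST has already fallen below 3xULN is left out of the Hy's Law table

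*SAP*

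**What the plan says.** SAP 10.3.1 plans a table of potential Hy's Law cases by treatment group. The definition is ALT or AST at least 3xULN with coexisting total bilirubin at least 2xULN, "in the absence of ≥2xULN ALP, with no alternative explanation for the biochemical abnormality". A timing rule follows: "a subject must experience the elevation in bilirubin and ALT or AST at the same visit". The one example has bilirubin raised first; the later "elevation in ALT (or AST) at a subsequent visit has not fulfilled the Hy's law criteria". No time window is given, and nothing is said about several samples belonging to one liver episode.

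The protocol has no same-visit condition. Section 6.3.1 speaks of ALT or AST at least 3xULN "and coexisting total bilirubin" of at least 2xULN. Section 11.1.1.3 uses the same adjective and says that potential Hy's Law "must ALWAYS be reported to UCB as an AE of special interest". Neither section says how close in time the two elevations must be.

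The protocol does expect repeated sampling. Section 11.6.1 requires initial abnormal liver tests to be repeated, and for most PDILI categories Table 11-3 asks for "Monitoring of liver chemistry values at least twice per week until values normalize, stabilize, or return to within baseline values".

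SAP 10.3.1 also plans a summary of subjects meeting the PDILI criteria, which "during the Treatment Period (scheduled and unscheduled visits) will be provided following the UCB standard table shell for PDILI Data", together with listings of PDILI data. The period covered by the Hy's Law table itself is not stated.

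**The concern.** Under the protocol's own follow-up, one liver episode produces several samples on different dates. ALT/AST and bilirubin need not peak together. Section 6.3.1 requires IMP to be stopped at ALT or AST of at least 5xULN, so a later sample with lower ALT/AST and higher bilirubin is foreseeable. A rule that scores each visit in isolation cannot join the two halves of such an episode.

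At stake is the completeness of the by-arm liver count. The adverse event outputs in SAP 10.2 include no summary of events of special interest, so the Hy's Law table is the only planned summary that labels these cases as such by treatment group. A sequential case would instead appear in PDILI rows labelled with bilirubin below 2xULN. A reader of the summary tables alone would see it as a transaminase elevation without a bilirubin rise.

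**Working it through.** The plan states no figure on this point, so there is nothing to reproduce. The check applies the SAP rule to illustrative sequences. Days, laboratory values and window lengths are assumptions; only the thresholds come from the documents.

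Rule as written: count the subject if any single sample has ALT or AST ≥3xULN and bilirubin ≥2xULN and ALP <2xULN. ALP is set at 1xULN throughout. Each pair below is ALT / bilirubin in multiples of ULN.

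| Sequence | Samples | Same-visit rule |
|---|---|---|
| A: together | day 0: 6 / 2.5 | counted |
| B: bilirubin later, ALT still ≥3 | day 0: 6 / 1.2; day 4: 4 / 2.3 | counted |
| C: bilirubin later, ALT now <3 | day 0: 6 / 1.2; day 4: 2.6 / 2.3 | not counted |
| D: as C, slower | day 0: 6 / 1.2; day 4: 4 / 1.7; day 7: 3.2 / 1.9; day 11: 2.5 / 2.2 | not counted |
| E: bilirubin first (the SAP's pattern) | day 0: 2 / 2.2; day 4: 3 / 1.6 | not counted |
| F: far apart | day 28: 3.5 / 1; day 84: 1 / 2.1 | not counted |

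B against C isolates the point. The order and timing are the same; the only difference is whether ALT is still at or above 3xULN when bilirubin reaches 2xULN. The gap is therefore limited to C and D, and does not extend to every later bilirubin rise.

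Next, an episode rule: bilirubin ≥2xULN at the same sample as, or at a later sample after, ALT/AST ≥3xULN, with a maximum gap of 7, 14 or 30 days (assumed).

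- A and B: the gap is 0 days; counted under every cap.
- C: the gap is 4 − 0 = 4 days; counted under every cap.
- D: measured from the last raised ALT the gap is 11 − 7 = 4 days, which is counted under every cap. Measured from the first it is 11 − 0 = 11 days, which passes the 14- and 30-day caps but not the 7-day cap.
- E: bilirubin comes first, so it is not counted, in line with the SAP's example. A window open in both directions would count it, because the two elevations are 4 days apart.
- F: the gap is 84 − 28 = 56 days; not counted under any of the three caps.

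D shows that the starting point of the gap has to be stated as well as its length.

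Finally, the period. Under SAP 3.2.2.2 the Treatment Period ends at the EDV for subjects who discontinue. The PDILI criteria summary is confined to the Treatment Period. If the Hy's Law table shares that limit, a day-11 sample as in D could fall outside it once IMP has been stopped. An episode rule would then still miss the case unless the later samples were expressly included.

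**The case against.** The strongest reply is that *coexisting* in ordinary use means present together. On that reading C and D, which never show both thresholds in one sample, do not meet the protocol's definition either, and the SAP has merely spelled it out. This stands as far as it goes. A reader might infer that the SAP contradicts the protocol, or that a case reportable as an event of special interest is certain to be lost from the table. Neither follows, because the second inference needs a sequential meaning that Protocol 11.1.1.3 does not state. What remains is that the term is undefined and the SAP has chosen its narrowest reading.

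Three further replies also hold:

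- Twice-weekly sampling does not clearly apply to every raised ALT/AST. For 3x to below 5xULN with bilirubin below 2xULN and no symptoms, Table 11-3 shows testing as not mandatory. The table's merged cells are hard to read in the available text. A footnote also allows another agreed schedule.
- Frequent sampling gives the same-visit rule more chances to succeed, as B shows, and the PDILI summary takes in unscheduled visits.
- The subject does not disappear. ALT 6xULN with bilirubin 1.2xULN falls in two PDILI rows if there are no symptoms and ALT is at least twice baseline, and in the symptom row if symptoms are present. Subjects meeting these criteria are listed. Bilirubin of at least 1.5 mg/dL and ALT above 123 U/L are also flagged with subject numbers under SAP 10.3 and 14.1.2. Reporting under Protocol 11.1.1.3 and 11.6.1 is independent of the table.

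These replies limit the impact. None of them brings C or D into the Hy's Law table.

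**Conclusion.** The point holds in a limited form. SAP 10.3.1 omits from the Hy's Law table a subject whose bilirubin first reaches 2xULN at a later sample of the same episode, after ALT/AST has fallen below 3xULN. No other section of the SAP relaxes this.

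The size is one descriptive table and, per occurrence, one subject. If the table would otherwise be empty, one such subject is the difference between none and one. A reader might want an expected number of missed cases, but the documents give no rate of Hy's Law events or of this sequence. The study also ended early (SAP 3.9), so the planned 400 subjects cannot be assumed either.

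A reader might also infer that the omission is the same whatever analysis period is used. It is not: for a subject who discontinues, the end of the Treatment Period at the EDV may remove the later sample for a separate reason, and both have to be dealt with.

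The conclusion rests on reading *same visit* literally and on follow-up samples carrying different visit dates. It is a worthwhile low-cost improvement to the safety summary and does not touch the efficacy conclusions.

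**What to change.** In SAP 10.3.1, keep the same-visit row and add one supplementary row. It counts subjects with total bilirubin ≥2xULN at the same sample as, or at a later sample of the same episode after, ALT/AST ≥3xULN, with the ALP condition applied to that episode. Bilirubin-first sequences stay out, as in the SAP's example.

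The text should also state:

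- The episode starts at the first ALT/AST ≥3xULN and ends at the monitoring endpoint in Protocol Table 11-3 and 11.6.1.4, that is, when values are back to normal or baseline or are judged stable.
- The sponsor sets a maximum gap in advance and says whether it runs from the first or the last raised ALT/AST sample.
- Liver follow-up samples taken after the EDV are included in this row.

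The cost is one table row and a short derivation from laboratory data already collected for PDILI. The downside is that an occasional unrelated later bilirubin rise will be flagged and must be reviewed individually; the requirement that there be no alternative explanation already calls for such review.
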